### **12.3 Other safety measurements**

#### **12.3.1 Vital signs**

The Investigator or designee should measure all vital signs (BP, temperature [oral, axillary, or otic], and pulse rate) after the subject has been sitting for at least 5 minutes, and the subject should remain seated during the measurements. At Baseline and at Week 16, vital signs will be measured prior to IMP administration and then at approximately 30 minutes and 1 hour after dosing. At all other visits, vital signs will be measured only once prior to dosing.

### **12.3.2 Body weight and height**

The Investigator or designee will measure the height of the subject with shoes removed in meters and the weight of the subject in kilograms. The same scale should be utilized throughout the study where possible.

### **12.3.3 Physical examination**

The physical examination should be conducted by the Investigator or designee at the time points listed in [Table 5-1](#) and will include general appearance; ear, nose, and throat; eyes, hair, and skin; respiratory; cardiovascular; gastrointestinal; musculoskeletal; hepatic; neurological (including limb reflexes); and mental status. Findings considered clinically significant changes since the physical examination at the Screening Visit will be recorded as AEs.

### **12.3.4 12-lead electrocardiogram**

The Investigator or designee will perform the ECGs which will be read centrally. Full details of ECG recording will be provided in the ECG Manual.

### **12.3.5 Assessment and management of TB and TB risk factors**

All subjects will be assessed for TB at Screening and at the time points specified in the schedule of study assessments ([Table 5-1](#)) through physical examination for signs and symptoms of TB, chest x-ray ([Section 12.3.5.2](#)), laboratory testing ([Section 12.3.5.1](#)), and subject questionnaire ([Section 12.3.5.3](#)).

At Screening, all subjects will have an IGRA test (QuantiFERON TB Test is recommended), a chest x-ray (unless already performed within 3 months of Screening) and examination for signs and symptoms of TB. In addition, each subject will complete a TB questionnaire directed at potential exposure to TB and symptoms of TB.

For the purposes of this study, TB definitions are as follows:

a. Known TB infection:

- Active TB infection or clinical signs and symptoms suspicious for TB (pulmonary or extra-pulmonary).
- History of active TB infection involving any organ system or findings in other organ systems consistent with TB infection, unless adequately treated and proven to be fully recovered upon consult with a TB specialist.
- Any evidence by radiography or other imaging modalities consistent with previously active TB infection that is not reported in the subject's medical history.

b. High risk of acquiring TB infection:

- Known close exposure to another person with active TB infection within the 3 months prior to Screening.
- Time spent in a healthcare delivery setting or institution where individuals infected with TB are housed and where the risk of transmission of infection is high.

---

c. Latent TB infection (unless appropriate prophylaxis is initiated at least 4 weeks prior to IMP dosing and continued to completion of prophylaxis):

- The absence of signs, symptoms, or physical findings suggestive of TB infection with a positive IGRA test (or 2 indeterminate IGRA test results) and a chest x-ray (or other imaging) without evidence of TB infection. If the result of the IGRA test is indeterminate, the particular IGRA test previously performed may be repeated once; if positive or indeterminate on retest, the subject may not be randomized to IMP without further evaluation by a TB specialist and discussion with the Study Physician, if LTBI is identified. The retest must be done during the protocol-defined Screening window.
- Note: If available, respiratory or other specimens must also be smear and culture negative for TB (Center for Disease Control diagnosis of LTB infection; <http://www.cdc.gov/TB/topic /testing/default.htm>).

[figure not shown]
d. NTMB infection is defined as a clinical infection caused by mycobacterial species other than those belonging to the *Mycobacterium tuberculosis* complex.

e. Tuberculosis test conversion:

- A positive IGRA result for the current test when previous IGRA test results were negative. All subjects with TB test conversion must immediately stop IMP administration and be referred to a TB specialist for further evaluation. Confirmed TB test conversions should be classified as due to LTBI, active TB infection, or NTMB, and reported to the UCB PS function.

Subject eligibility, retesting requirements, and treatment requirements are presented in [Figure 12-1](#). A schematic diagram of TB test results during the study is presented in [Figure 12-2](#).

**Figure 12-1: Schematic diagram of TB test results and study eligibility**

CDC=Center for Disease Control; IGRA=interferon-gamma release assay; LTBI= latent tuberculosis infection; TB=tuberculosis; WHO=World Health Organization

a IGRA retest must be done during the protocol-defined Screening window.

b Subject has a past history of active TB involving any organ system unless adequately treated according to WHO/CDC therapeutic guidance and proven to be fully recovered upon consult with a TB specialist. Subjects who have recently (no more than 12 months prior to Screening) completed full treatment course of prophylaxis for LTBI are allowed. Prophylaxis should be in accordance with WHO/CDC guidelines and TB specialist judgment based on the origin of infection.

c Subjects with LTBI may enter the study only after they have completed at least 4 weeks of appropriate prophylactic therapy and thereafter, will continue and complete the entire regimen.

**Figure 12–2: Schematic diagram of TB test results during the study**

ASAP=as soon as possible; IGRA=interferon-gamma release assay; LTBI=latent tuberculosis infection; TB=tuberculosis

a IGRA retest must be done ASAP and prior to the next dose.

b Subjects with LTBI may continue the study only after they have completed at least 4 weeks of appropriate prophylactic therapy and thereafter, will continue and complete the entire regimen.

### **12.3.5.1      Tuberculosis assessment by IGRA**

During conduct of the study, the TB assessment by IGRA (QuantiFERON TB Test is recommended) will be performed as described in [Table 5-1](#) for all subjects. The test results will be reported as positive, negative, or indeterminate. Positive and indeterminate TB test results that occur during the course of the study must be reported as an AE and appropriately updated once the final diagnosis is known (eg, active TB, latent TB, or false positive TB test). UCB also recommends that a TB specialist be consulted where TB (latent or active) is suspected or if there are doubts regarding test results. If latent or active TB is identified, subject must undergo appropriate study-specified withdrawal procedures. The retest during Screening must be done during the protocol-defined Screening window.

### **12.3.5.2      Chest x-ray for tuberculosis**

A plain posteroanterior chest x-ray must be performed in the Screening Period unless one has been performed within 3 months prior to the Screening Visit. The chest x-ray (or, if done, Computed Axial Tomography [CAT] of the chest) must be clear of signs of TB infection (previous or current) before first IMP administration. All chest imaging (particularly x-rays) should be available for review by the Investigator before randomization of the subject. The chest x-ray reading should be repeated if the TB test was confirmed positive. If the second read of the pretreatment chest x-ray is confirmed to be clear, the subject may be included in the study 4 weeks after the start of the TB prophylactic treatment. If the pretreatment chest x-ray is not available for a re-read, it should be repeated after notification to the radiologist that this subject is IGRA positive and confirmed to be clear for signs of TB.

The chest imaging must be negative for any old or recent TB infection as determined by a qualified radiologist and/or pulmonary physician. Any new clinically significant findings post Baseline on chest x-ray must be documented in the source documents and the eCRF as an AE.

### **12.3.5.3      Tuberculosis questionnaire**

The questionnaire “Evaluation of signs and symptoms of tuberculosis” should be used as a source document. The questionnaire will be completed as described in [Table 5-1](#). The questionnaire will assist with the identification of subjects who may require therapy for TB. A subject who answers “Yes” to the question [REDACTED]

[REDACTED] at Screening is excluded. A “Yes” response to any of the other questions within the questionnaire at Screening should trigger further careful assessment to determine if subject has LTB or active TB (see Exclusion Criterion #10 in [Section 6.2](#)). A “Yes” response to any of the questions during the study should trigger further assessments to determine if the subject has either LTB or active TB infection.

### **12.3.5.4      Tuberculosis management**

#### LTB infection and active TB identified during study

During the study, subjects who develop evidence of LTB infection or active TB must immediately stop further administration of IMP and will be referred to an appropriate TB specialist (pulmonologist or infectious disease specialist) for further evaluation. Evidence of LTB infection is defined as subject’s IGRA test converts to positive or indeterminate (and confirmed indeterminate on repeat), or the subject’s questionnaire or history and physical

---

indicates that TB infection or exposure may have occurred. Evidence of active TB includes, in addition to the aforementioned tests, signs and symptoms of organ involvement. In either situation, the subject should be carefully assessed by a TB specialist for active TB. Subjects diagnosed with active TB should be withdrawn from the study and receive appropriate TB or prophylaxis therapy.

If a TB specialist excludes an active TB infection, the subject can proceed with the IMP no earlier than 4 weeks after the start of an appropriate prophylactic therapy.

Any presumptive diagnosis or diagnosis of a TB infection is a reportable event. Confirmed active TB must be reported as an SAE. The Investigator is to complete and submit the TB follow-up form provided.

The subject should be transferred to the care of his/her physician and managed according to the best available standard of care. Subjects identified as having converted to active TB during the study must be withdrawn and scheduled to return for the ET Visit as soon as possible but no later than the next scheduled study visit and complete all ET Visit assessments.

The subject should be encouraged to complete a SFU Visit (20 weeks after the final dose of IMP).

If infection with NTMB is identified during the study, the same procedure as for active TB acquired during the study must be followed.

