- positive for hepatitis C antibody (anti-HCV antibody), and
- positive via a confirmatory test for HCV (for example, HCV polymerase chain reaction)

9. Subject has received any live (includes attenuated) vaccination within the 8 weeks prior to the Baseline (eg, inactivated influenza and pneumococcal vaccines are allowed, but nasal influenza vaccination is not permitted).
10. Subject has received Bacillus Calmette-Guerin (BCG) vaccinations within 1 year prior to the Baseline Visit.

11. Subject has known tuberculosis (TB) infection, is at high risk of acquiring TB infection, or has current or history of nontuberculous mycobacterium (NTMB) infection. A subject with latent tuberculosis (LTB) (a positive interferon gamma release assay [IGRA] and diagnosis confirmed by TB specialist) may be rescreened once and enrolled after receiving at least 4 weeks of appropriate LTB infection (LTBI) therapy and if no evidence of therapy-related hepatotoxicity has occurred prior to the first injection (alanine aminotransferase [ALT]/aspartate aminotransferase [AST] remain  $\leq 3$  times upper limit of normal [ULN]).

Subject has a past history of active TB involving any organ system unless adequately treated according to World Health Organization/Center for Disease Control and Prevention therapeutic guidance and proven to be fully recovered upon consult with a TB specialist.

Refer to [Section 12.3.5](#) for details on determining full TB exclusion criteria.

12. Subject has a history of a lymphoproliferative disorder including lymphoma and/or current signs and symptoms suggestive of lymphoproliferative disease.

13. Subject has a diagnosis of inflammatory conditions other than PSO or PsA including, but not limited to RA, sarcoidosis, systemic lupus erythematosus, and reactive arthritis. Subjects with a diagnosis of Crohn's disease, ulcerative colitis, or other inflammatory bowel disease (IBD) are allowed as long as they have no active symptomatic disease at Screening or Baseline.

14. Subject had acute anterior uveitis within 6 weeks of Baseline.

15. Subjects with fibromyalgia or osteoarthritis symptoms that in the Investigator's opinion would have potential to interfere with efficacy assessments.

16. Subject has any active malignancy or history of malignancy within 5 years prior to the Screening Visit EXCEPT treated and considered cured cutaneous squamous or basal cell carcinoma, or in situ cervical cancer.

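### The on-study TB provisions for stopping, Early Termination and restarting study drug do not agree across Section 6.3, Section 12.3.5 and Figure 12-2

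*Protocol*

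**What the plan says.** All references are to the protocol.

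- **Section 12.3.5.4** covers TB identified during the study. It counts as evidence of latent TB an IGRA conversion, a confirmed indeterminate IGRA, or a questionnaire or history and physical that "indicates that TB infection or exposure may have occurred". Such evidence requires an immediate stop of study drug and specialist referral. Once active TB is excluded, the only restart stated is from four weeks after prophylaxis is started.
- **Section 12.3.5.3**: an affirmative questionnaire answer during the study "should trigger further assessments to determine if the subject has either LTB or active TB infection". No stop is stated.
- **Section 12.3.5(b)** lists known close exposure as high risk of acquiring TB, a category separate from latent TB in (c).
- **Section 12.3.5(e)** requires a stop on test conversion, meaning a positive IGRA after negative ones.
- **Section 12.3.5.1** gives, as examples of the final diagnosis after a positive or indeterminate on-study test, "active TB, latent TB, or false positive TB test". It sends latent as well as active TB to withdrawal procedures.
- **Section 6.3, criterion 9**: suspected new latent TB leads to immediate discontinuation of study drug and an Early Termination Visit. Permanent withdrawal follows for active TB, or for latent TB where prophylaxis is not started, is stopped early or is not complied with.
- **Figure 12-2, footnote b** lets subjects with latent TB continue once four weeks of prophylaxis are completed.
- **Section 12.3.5(c)** defines latent TB, in the absence of signs and symptoms, "with a positive IGRA test (or 2 indeterminate IGRA test results) and a chest x-ray (or other imaging) without evidence of TB infection".
- **Section 6.2, exclusion criterion 11** describes latent TB as "a positive interferon gamma release assay [IGRA] and diagnosis confirmed by TB specialist".

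**The concern.** These passages tell sites when to stop study drug, whether an Early Termination Visit follows and when dosing may resume. Followed literally, they give different instructions for the same subject. A subject with a possible exposure and no sign of infection is either assessed or stopped, depending on the section consulted. If that subject is stopped, the only route back described in 12.3.5.4 runs through prophylaxis, which presupposes an infection that may have been ruled out.

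The statistical interest is that Section 14.3.1.1 makes discontinuation of study treatment before Week 16 an intercurrent event and treats it as nonresponse. If a TB stop counts as discontinuation, a subject's ACR50 outcome could depend on which section the site followed. With about 150 planned sites, uniform reading cannot be taken for granted.

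**Working it through.** **1. The same subject under each provision**

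| Subject | Provisions side by side | Agreement |
|---|---|---|
| On study, possible exposure reported, no IGRA conversion | 12.3.5.3: assess. 12.3.5(b): exposure is high risk, not latent TB. 12.3.5(e): no conversion, so no stop under this item. 12.3.5.4: evidence of latent TB, immediate stop, restart only via prophylaxis. | No |
| On study, positive IGRA later judged false | 12.3.5(e) and 12.3.5.4: stop. 12.3.5.1: false positive is a possible final diagnosis. 12.3.5.4: restart only via prophylaxis. Figure 12-2 footnote b: speaks only of subjects with latent TB. | Stop agrees; no way back in the surviving text |
| On study, latent TB, active TB excluded, prophylaxis taken | 12.3.5.1: withdrawal procedures. Criterion 9: discontinue and Early Termination Visit. 12.3.5.4: restart from four weeks after prophylaxis starts. Figure 12-2 footnote b: continue after four weeks completed. | No |
| Screening, two indeterminate IGRAs | 12.3.5(c): latent TB. Criterion 11: not mentioned. | Narrow gap |

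On the third row, Section 8.3 describes the Early Termination Visit as the visit for subjects leaving the study. The lead-in to the list containing criterion 9 instead asks subjects withdrawn from study drug to keep attending scheduled visits.

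A cross-reference is also wrong. Section 12.3.5.3 points to exclusion criterion 10 for TB, but number 10 concerns BCG vaccination and TB is number 11.

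**2. Timing against the primary endpoint**

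- Scheduled TB questionnaires after the first dose (Section 8.2): Weeks 12, 24, 36 and 52. Only Week 12 precedes Week 16.
- Scheduled post-Baseline IGRA: Week 48 only.
- The main scheduled trigger before the endpoint is therefore the questionnaire, or the history and physical, which is where 12.3.5.3 and 12.3.5.4 part.
- Procedures precede dosing (Table 5-1, footnote f), so a Week 12 stop removes the Week 12 dose. Table 7-1 gives active bimekizumab at Baseline and Weeks 4, 8 and 12 before the Week 16 assessment, so this is one dose of four.
- Earliest restart under 12.3.5.4: 12 + 4 = Week 16, if prophylaxis starts the same day.

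**3. Effect on the primary comparison**

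Inputs from Section 14.9.1: 420 and 280 subjects, response rates 43.8% and 16%.

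Reproducing the plan's figures:

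- Odds ratio = (0.438/0.562)/(0.16/0.84) = 4.09, as stated.
- Corrected difference = 0.278 − ½(1/420 + 1/280) = 0.2750.
- Pooled rate = (0.438×420 + 0.16×280)/700 = 228.8/700 = 0.327. Null standard error = √[0.327×0.673×(1/420 + 1/280)] = 0.0362.
- Alternative standard error = √(0.438×0.562/420 + 0.16×0.84/280) = 0.0327.
- z = (0.2750 − 1.96×0.0362)/0.0327 ≈ 6.25, so power exceeds 99%, as stated.

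Assumed loss of responders to TB stops (no rate is given in the documents):

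| Responders lost | Difference | Odds ratio | Power |
|---|---|---|---|
| 0% | 27.8 points | 4.09 | >99% |
| 1%, both arms | 27.5 points | 4.07 | >99% |
| 10%, both arms | 25.0 points | 3.87 | >99% |
| 10%, bimekizumab only | 23.4 points | – | >99% |

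For scale, suppose 0.5% to 2% of the 700 bimekizumab and placebo subjects report possible exposure by Week 12 (assumed). That is 3.5 to 14 subjects. Only expected responders can change outcome: 228.8×0.005 = 1.1 to 228.8×0.02 = 4.6, or about 1 to 5, if exposure is unrelated to response and every stop counts as discontinuation.

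**The case against.** A reader might infer that the protocol holds three incompatible definitions of latent TB, so that eligibility varies by site. The documents do not support this. Criterion 11 is not free-standing: it refers to Section 12.3.5 "for details on determining full TB exclusion criteria". After an indeterminate test with a positive or indeterminate retest, 12.3.5(c) says "the subject may not be randomized to IMP without further evaluation by a TB specialist". The wording in 12.3.5.4 is an on-study trigger for stopping and referral, not a diagnosis, and it does not govern eligibility. A trigger broader than a diagnosis is not in itself a contradiction. This objection stands, and it reduces the eligibility issue to the two-indeterminate gap and the wrong criterion number.

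It can also be said that 12.3.5.3 and 12.3.5.4 run in sequence: an affirmative answer prompts assessment, and a stop follows only if that assessment points to infection or exposure. This reading is possible, but the text does not state it. Section 12.3.5.4 lets the questionnaire itself supply the evidence and makes the stop immediate. Criterion 9 does separate suspicion from diagnosis when it comes to permanent withdrawal, but it still attaches an Early Termination Visit to suspicion alone.

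The flowchart in Figure 12-2 is not shown, and a route for a subject found uninfected may be drawn there. The point about the missing route is therefore limited to the surviving text.

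Finally, a reader might infer that subjects could restart before the primary endpoint, or that the primary result is at risk. From the scheduled Week 12 check the earliest restart is Week 16, so only an unscheduled earlier stop could lead to restart before it. The estimand names discontinuation and does not say whether a temporary TB hold qualifies; the SAP, not at hand, may settle that.

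**Conclusion.** The point holds as an inconsistency in on-study conduct. The stop after a questionnaire-only signal, the Early Termination Visit and the continuation of subjects with latent TB read differently in Sections 6.3, 12.3.5(b), 12.3.5(e), 12.3.5.1, 12.3.5.3, 12.3.5.4 and Figure 12-2 footnote b. The surviving text also leaves a subject found uninfected without a stated way back. Taken literally, an uninfected subject could be stopped, or could resume only through prophylaxis, depending on the section followed.

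The eligibility gap is secondary and narrow. The link to the primary endpoint is conditional: a Week 12 stop becomes nonresponse only if it counts as discontinuation. The number affected is not in the documents. On the assumed 0.5% to 2% exposure rate, about 1 to 5 responder outcomes could change, and power stays above 99% even in the far heavier losses tabulated. The passages should be corrected for consistent conduct; neither the sample size nor the primary conclusion is in question.

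**What to change.** Reconcile exclusion criterion 11, withdrawal criterion 9, Sections 12.3.5(b), (c) and (e), 12.3.5.1, 12.3.5.3 and 12.3.5.4, and Figure 12-2, so that eligibility, stopping, the Early Termination Visit and restart each read one way. The reconciled text should say how it classes:

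- a questionnaire-only or history-only signal;
- a positive test later judged false;
- two indeterminate results at Screening.

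Correct the pointer in Section 12.3.5.3 from criterion 10 to criterion 11. Confirm in the SAP, if it is not already there, whether a temporary TB hold before Week 16 counts as discontinuation for the primary estimand.

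Which clinical rule applies is for the sponsor and its clinical advisers to decide. The cost is protocol wording. No new procedure is needed, since specialist assessment of on-study evidence is already required.

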#### **12.3.6      Pregnancy testing**

Pregnancy testing will consist of serum testing at Screening for all women of childbearing potential. The pregnancy test will be urine at all other visits.

The Screening Visit serum pregnancy test results must be negative and received and reviewed prior to randomization. A negative urine pregnancy test result should be obtained immediately prior to each administration of IMP at the visits specified in [Table 5-1](#). Pregnancy tests should be administered to all female subjects of childbearing potential, regardless of their use of birth control.

